30] Aloe Vera also inhibits the cyclooxygenase pathway, dropping the production of prostaglandins, thus decreasing the inflammation. [31]

Some studies stated the use of aloe Vera in dentistry in numerous areas like disinfecting dental unit water network, [32] gutta-percha sterilization, [33] antiseptic effect on candida albicans, [34] Aphthous stomatitis management, [35] as an ingredient in toothpastes [36-37] and mouthwashes.[28] Up to date, limited studies have been reported in relation to the effect of topical application of aloe Vera in the periodontal pocket for periodontal disease management. [38]

The null hypothesis is that flurbiprofen has no statistically significant effect in comparison to Aloe Vera gel as an adjunctive to SRP in the reduction of periodontal pockets in smoking patients with chronic periodontitis stage III.

Aim of this study:

This study aims to evaluate clinically the effect of flurbiprofen gel in comparison to Aloe Vera gel as adjunctive to SRP in the reduction of periodontal pockets in patients with chronic periodontitis stage III in smoking patients.

Materials and methods:

Participants:

This study was conducted at the Department of Oral Surgical Sciences, Division of Periodontology, Faculty of dentistry, Beirut Arab University (BAU)-Lebanon after approval of Institutional Review Board (IRB) with trial NO 2022-H-0100-D-R-0487. Patients were first briefed about the study and written consent was obtained. The study was performed in compliance with the principles of the Declaration of Helsinki.

The estimated sample size will be calculated according to <http://epitools.ausvet.com.au/>, by taking the means of clinical attachment level at 3 months in both groups from a previous similar study conducted by (39) where mean for test site = 5.75 ± 0.35 and mean for control site is = 6.4 ± 0.3 , where the variance will be calculated to be 0.35, assuming a confidence level of 95% and a study power of 80%. The calculated sample size will be 14 patients per group (28 operating sites). However, as some dropouts may be expected, a minimum of 20 patients per group were recruited

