- Group one (G1): comprised of 20 patients who received treatment involving the application of flurbiprofen gel as an adjunct to scaling and root planing. Specifically, on the test site of each patient, one milliliter of 2.5% flurbiprofen gel was applied, while on the contralateral side, scaling and root planing were performed as the control intervention.
- Group two (G2): comprised of 20 patients who received treatment involving the application of aloe Vera gel as an adjunct to scaling and root planing. Specifically, on the

test site of each patient, one milliliter of 98% aloe Vera was applied, while on the contralateral side, scaling and root planing were performed as the control intervention.

- Group three (G3): The intervention involved applying flurbiprofen gel on one site, while the contralateral side received an application of 98% aloe vera.

Clinical measurements:

The clinical periodontal parameters were recorded by one blinded examiner from the mesio-buccal, mid-buccal, disto-buccal, disto-lingual, mid-lingual, and mesio-lingual surfaces of each tooth using a colour coded periodontal probe (PQWBR - Hu Friedy Mfg. Inc. Chicago, IL, USA): and checked by another blinded examiner. Examiners were calibrated to ensure intra-examiner as well as inter-examiner agreement when measuring PD and CAL values. Fifteen patients were examined twice before the trial, 24 hours apart. Calibration was considered accepted if both measurements at the baseline and after 24 hours were similar to one mm at the 90% level.

In this clinical study, various clinical measurements were undertaken to assess the oral health status of the participants. These measurements included the clinical attachment level (CAL), probing depth (PD), plaque index (PI), gingival index (GI), and bleeding on probing (BOP).

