Initially, the PI and GI were measured at four sites per tooth, with gingival bleeding being recorded within 15 seconds. To prevent misinterpretation of gingival bleeding as BOP, patients were asked to rinse with water after this assessment. Subsequently, all teeth were probed at six different locations per tooth. CAL was determined as the distance from the cemento-enamel junction (CEJ) to the pocket depth, while the PD was measured as the distance from the gingival margin to the base of the pocket. BOP was recorded 15 seconds after probing. It is important to note that these clinical parameters were recorded at the baseline (1st visit) before the treatment and were repeated at the fourth week (2nd visit), eighth week (3rd visit), twelfth week (fourth visit), and at 6 months (5th visit). During this observation period, participants received reinforcement of plaque control and additional instructions to maintain optimal oral hygiene

Preparation of gels:

Aloe Vera:

Aloe vera gel used in this study was 98% aloe vera[®] gel concentration (Avivir; Denmark) and 2% normal saline. Commercial preparation method of 98% concentration of aloe vera gel was washing the ripe aloe Vera leaves thoroughly under water and cutting off their skin. Each leaf was cut into several pieces and seeping gel from the pieces were collected in a sterile container and stored at 4°C until the time of application. [38]

Flurbiprofen:

Gel was made of 20% poloxamer and 10% ethanol as an Optimum formulation with sustained release up to 48 hours and a reasonable sol gel transition phase.

Statistical analysis:

Statistical analysis was done using SAS 9.4 Software (SAS Institute Inc., Cary, NC, USA). Means and standard deviations (SD) were calculated for all continuous variables (periodontal parameters: CAL, PD, BOP, GI, PI) at the baseline, fourth week, eighth week, and twelfth week and 6 months. Repeated linear mixed-effects models (PROC MIXED in SAS) were used to examine the changes in all periodontal parameters over the five-time points within each group and between groups. An unstructured covariance matrix was used, residual plots were visually reviewed to check model fit, and extreme outliers were eliminated using the restricted likelihood distance. A Tukey-Kramer 8 correction was applied to all pairwise comparisons. One-way ANOVA was used to examine group differences in PD reduction and CAL. A p-value of 0.05 was considered statistically significant.

References:

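### No primary parameter, visit or contrast is named and the Tukey-Kramer family is undefined, so the error rate of a claim that one gel is better cannot be determined from the plan

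*Combined protocol and SAP*

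**What the plan says.** All points are in the combined protocol and SAP.

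- **Hypothesis (end of Introduction).** There is a single null hypothesis, worded as follows: "flurbiprofen has no statistically significant effect in comparison to Aloe Vera gel as an adjunctive to SRP in the reduction of periodontal pockets". The outcome is pocket reduction; no visit is given.
- **Sample size (Participants).** The calculation was made "by taking the means of clinical attachment level at 3 months in both groups". This is a different parameter, and it is not labelled primary.
- **Measurements (Clinical measurements).** "These measurements included the clinical attachment level (CAL), probing depth (PD), plaque index (PI), gingival index (GI), and bleeding on probing (BOP". After baseline they "were repeated at the fourth week (2nd visit), eighth week (3rd visit), twelfth week (fourth visit), and at 6 months (5th visit". None of the five parameters and none of the four post-baseline visits is given priority.
- **Analysis (Statistical analysis).** Repeated mixed models are fitted to all parameters over the five time points, both within and between groups. A Tukey-Kramer "correction was applied to all pairwise comparisons", with no statement of which means form the family. One-way ANOVAs of group differences in PD reduction and CAL are added, with no visit. The only decision rule is "A p-value of 0.05 was considered statistically significant". No adjustment across parameters is stated.

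**The concern.** The trial has one hypothesis but no single test that answers it. The plan offers three anchors: pocket reduction in the hypothesis, CAL at 3 months in the sizing, and 6 months as the last visit. It also offers two analyses of PD and CAL, the mixed model and the ANOVA.

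Tukey-Kramer acts on pairs of means inside one model. It does not act across the separate models for CAL, PD, BOP, GI and PI, and it does not reach the ANOVAs, which lie outside the mixed model. A claim that one gel is better could therefore rest on whichever parameter, visit or method crosses 0.05, and a reader of the results could not attach an error rate to it.

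The contrast is open as well. Flurbiprofen can be compared with Aloe Vera between the test sites of G1 and G2, within patients in G3, or by both combined, and the plan does not say which.

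**Working it through.** **1. The plan's own figure.** Inputs from Participants: means 5.75 and 6.4 (difference 0.65), variance 0.35, 95% confidence, 80% power.

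n = 2 × 0.35 × (1.960 + 0.842)² / 0.65² = 13.004, rounded up to 14 per group. This matches the plan. The sizing thus assumes one two-sided comparison of CAL at 0.05, with no allowance for further tests.

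**2. What the Tukey family could be.** The plan has 3 groups and 5 time points. Critical |t| is the studentized range quantile divided by √2, here with 57 df (3 × 20 − 3).

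- Three groups at one visit (3 pairs): |t| = 2.41.
- All 15 group-by-visit means of one parameter (15 × 14 / 2 = 105 pairs): |t| = 3.54.

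The wording fits either.

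**3. Chance of at least one false between-group result.** Simulation under no treatment effect: 3 groups of 20, one value per patient, parameter and visit, equal correlation among parameters, and correlation 0.7 between visits. Each setting has 12,000 simulated trials (Monte Carlo standard error at most 0.5 percentage points). All correlations are assumptions.

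| Correlation between parameters | Five parameters, one visit, 3-group family | Five parameters, four visits, 3-group family | PD and CAL, one visit, 3-group family | PD and CAL, four visits, 3-group family | Five parameters, four visits, 15-mean family |
|---|---|---|---|---|---|
| 0 | 22% | 52% | 9% | 25% | 4.0% |
| 0.3 | 22% | 49% | 10% | 24% | 3.7% |
| 0.5 | 19% | 45% | 9% | 24% | 3.6% |
| 0.7 | 16% | 37% | 8% | 22% | 2.9% |
| 0.8 | 13% | 33% | 8% | 21% | 2.9% |
| 0.9 | 11% | 27% | 8% | 19% | 2.1% |

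Exact check at independence, one visit: 1 − 0.95⁵ = 22.6% and 1 − 0.95² = 9.75%.

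Sensitivity to the between-visit correlation (five parameters, four visits, 3-group family, parameter correlation 0 to 0.9): 58% to 31% at 0.5, and 41% to 20% at 0.9. With the 15-mean family and everything independent, the rate is 4.6%.

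The simulation leaves out the ANOVAs and the within-group time contrasts. It treats the comparison as three independent groups, not as split-mouth.

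**4. Price of the wide family.** Using the plan's sizing inputs with 20 per group, the noncentrality is 0.65 / √0.35 × √(20/2) = 3.47. With 57 df, power is:

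- 93% for a single named test (|t| > 2.00)
- 85% with the 3-group family (|t| > 2.41)
- 48% with the 15-mean family (|t| > 3.54)

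This is illustrative, because the 0.65 is a difference between test and control sites, not between the two gels. It also depends on the plan's variance of 0.35. The SDs quoted beside it give (0.35² + 0.3²)/2 = 0.106, and with that value all three powers exceed 99%.

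**The case against.** The strongest case on the other side is that the plan does correct for multiplicity and makes no trial-wide promise.

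- **A reader might infer that the false-positive rate is at least three times a stated 5%.** The documents do not support that. The 0.05 is a per-test threshold, and no familywise rate is claimed. Threefold is also not a lower bound. On the 3-group, one-visit reading the rate falls below 15% once the correlation between parameters exceeds about 0.7. On the 15-mean reading it is below 5% over all 20 parameter-by-visit cells.
- **A reader might infer that every parameter at every visit is tested at an unadjusted 0.05.** The plan instead describes repeated mixed models with Tukey-Kramer on the pairwise comparisons, and it names no separate test at each visit.
- **A reader might infer that any of 20 results can reject the null hypothesis.** The hypothesis concerns pocket reduction, and PI, GI and BOP do not test it. With PD and CAL only, each held at 5%, the ceiling is about 10%.

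These objections stand and remove any single inflation figure. They do not settle the matter. Even with PD and CAL alone the rate reaches 19–25% over four visits if Tukey covers only the groups. The ANOVAs carry no visit and lie outside the mixed model's family on any reading. The reading that keeps the rate below 5% is not the one the plan states; it is one of two that the wording allows.

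**Conclusion.** The concern holds as an indeterminacy. The primary parameter, visit, contrast and Tukey family are all unstated, and nothing is adjusted across parameters. Depending on how the wording is read, the chance of some false between-group result runs from about 2–5% (15-mean family) to 27–52% (3-group family, five parameters, four visits, between-visit correlation 0.7). The intermediate cases are 11–23% for five parameters at one visit, and 8–10% (one visit) or 19–25% (four visits) for PD and CAL.

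These figures rest on assumed correlations, three groups of 20 with no dropout, and only the between-group pairs at post-baseline visits. They do not establish a particular inflation, and a fixed multiple of 5% should not be quoted. This is more than missing detail, because following the plan as written lets the main claim rest on whichever test succeeds. The rating is should-fix rather than must-fix: a cheap improvement.

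**What to change.** - **Name one primary test** at two-sided 0.05: flurbiprofen versus Aloe Vera at 12 weeks (the 3-month point used for sizing), estimated from the mixed model with baseline as a covariate. Use PD reduction, because it matches the stated hypothesis, and test CAL at 12 weeks only if PD is significant. If the sponsor prefers CAL because the trial was sized on it, reverse the order.
- **Define the contrast.** State how G3, where both sites receive a gel, enters it, for example as within-patient information through a patient random effect alongside the G1 and G2 test sites.
- **Define the Tukey-Kramer family** for the remaining comparisons, listing the means it covers.
- **Label the rest as supportive:** PI, GI, BOP, the other visits and the one-way ANOVAs, with the visit of the ANOVAs stated.
- **Disclose timing.** Much of the document describes recruitment, measurement and analysis in the past tense. If data have been seen, report the choice of primary test as post hoc.

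The cost is SAP wording only, with no change to visits, measurements or sample size. The downside is small: isolated significant results on other indices or visits can no longer be claimed as confirmatory.
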